Monitoring CKD-PD smartphone and web applications: We will set 3 categories to be used by PD clinic staff when monitoring hydration metrics on the CKD - PD web application: normal, monitor, and action required. Based on criteria specified by KKU nephrologists, deviations in weight of >3% from baseline dry weight, BP>140/90, and ultrafiltration volume of <500 ml will be used as baseline parameters for triggering an outlier alert for action required, indicating that the patient's hydration metrics need to be reviewed. We will also set critical values for hydration metrics, which require patient to go directly to the emergency department. We expect that some patients will require different parameters for triggering an outlier alert. In order to address this issue, a study nephrologist will provide normal and action required values for weight, blood pressure, and ultrafiltration volumes for each patient, at the time of enrollment after reviewing previous values from their PD logbook. During the study, the patient's nephrologist will have the option to modify the notification parameters. Hydration metric values between normal and action required will be categorized as monitor status.

PD clinic staff nurses will receive a list of patients with action required alerts once a day. They will review the hydration metrics and contact the patient(s), ask about symptoms, and have the nephrologist review the data and case to determine need for clinical intervention.

PD patients will also have the ability to self-monitor using the visual display of hydration metrics on the CKD-PD app. Planned features to simplify patients understanding of their fluid status include color coded zones corresponding to the normal (green), monitor (yellow), and action required (red) categories. During training, patients will be instructed to contact the PD clinic if one or more of the hydration metrics indicate action required.

Planned research procedures: Our project has 5 research procedures, all of which will collect private, identifiable patient information.

1. *Monitoring for abnormal hydration metrics by PD clinic staff:* PD clinic staff will review the CKD-PD web application daily for outlier alerts. Outliers are determined based on the hydration metric parameters set by the nephrologist at enrollment. See 4.2.a.3 below.
2. *Clinical intervention for overhydration:* Change in medical treatment in response to OH detected by clinical symptoms or hydration metrics. Interventions may include a change in medications to treat OH such as anti-hypertensives or diuretics, dialysis prescription, dietary sodium/fluid restriction, referral for evaluation in clinic, or hospitalization. This information will be collected in the electronic PD clinic study log at the time of the clinical intervention.
3. *Unscheduled clinic contacts:* When patients in either group make an unscheduled contact with the PD clinic this will be recorded in the PD clinic electronic study log. Unscheduled clinic contact can also occur in the “app” group when PD clinic staff contact a patient in response to abnormal hydration metrics. Unscheduled contacts include any phone call, text, social media, or web app message, and unscheduled visit to the PD clinic or emergency department. The information collected included patient name/MR#, reason for contact, mode of contact, who initiated contact, date and time of day, and action taken. Unscheduled clinical interventions will be recorded at the time of the event.
4. *Scheduled clinic contacts:* Patients in both groups will have regularly scheduled clinic visits, typically bimonthly. Clinical interventions for OH made during this visit will be recorded in the electronic PD clinic study log. A medical record review will also occur at each visit to collect any other hospitalizations, complications, or clinical interventions that may have occurred in the interim.
5. *CKDNET database review:* In order to ensure all events have been captured, we will review the CKDNET database, which has all inpatient and outpatient visits, on a bimonthly basis.

Data collection overview

Data elements for analysis of covariates at enrollment: These will include: age, sex, educational level, cause of CKD, eGFR, co-morbidities (e.g. diabetes, hypertension, albumin level), previous hospitalizations for OH, smoking status, distance from clinic, months on PD, months of CKD-PD usage, and app user type (patient or surrogate). The source will be medical records and patient interview at time of enrollment.

Clinical interventions used: We will record the type of clinical intervention, patient symptom/hydration metric abnormality, whether it was occurred from a scheduled or unscheduled communication, and ordering clinician. This information will be recorded in an electronic study log at time of PD clinic visit, or time of communication to patients.

Outcome measures: Our primary outcome measure will be the incidence of clinical interventions for OH in 1 year from enrollment. Secondary outcome measures include OH-related complications

Drop out/Lost to follow up: The number of patients who drop out, are lost to follow up or died during the study period will be collected. This information will be collected from chart reviews and PD clinic communications and recorded in the electronic clinic study log.

PD clinic/patient communications: We will also collect data about communications between PD clinic staff patients or their surrogates by logging phone calls and messaging app contacts. This information will include who initiated the call, whether or not it resulted in a clinical intervention, the type of clinical issue, and mode of communication. This information will be recorded in the PD clinic electronic study.

Potential risks to participants: This study poses low risk to participants with regard to physical, psychological, social, cultural or legal aspects as both groups receive the same standard of care as currently provided to PD patients at the study site nephrology clinics, including routine clinic appointments, medications, dialysis prescriptions, dietary recommendations, educational and other community support networks, and urgent services e.g. phone contact to PD clinic, unscheduled clinic visits, and emergency care. We have identified some potential specific risks including data breaches, lost or malicious hacking of computers, loss of privacy, concern about change or access to PD care, over or under identification of overhydration, failure to detect life threatening outlier data points in a timely fashion, technology failure, communication failures and errors, and unintended consequences of using a new technology. Strategies to mitigate these risks are discussed below. Alternative strategies available to participants are the option to decline or withdraw from the research at any time.

Informed Consent and Assent

Informed consent: Trained research staff will obtain informed consent from all participants. [name] and [name] will oversee this process, including training of research staff and answering any questions from staff or participants as needed. The informed consent form and process will be approved by the Khon Kaen University Ethics Committee and the Partners Health Care/Massachusetts General Hospital Institutional Review Board. All participants will be informed that their participation is voluntary and does not in any way impact access to treatment or other resources for care, and they can drop out of the study at any time for any reason at all including no reason. Signed copies of the informed consent will be kept with study records, and a copy will be given to the participant.

Planned strategies to minimize potential risks: We will include the following general protections:

1. De-identify and summarize results from study logs and medical records prior to analysis when feasible.
2. Confirm all study staff successfully completed CITI ethics training.
3. Provide all written materials and descriptions of study activities in local language (Thai) at an appropriate literacy level.
4. We will obtain IRB approval for this proposed research through the Khon Kaen University Ethics Committee and the Partners Health Care/Massachusetts General Hospital Institutional Review Board. We will not begin enrollment until this has been secured.
5. We will use password protected, encrypted computers.
6. Access to study data will be limited to research team members

We have identified these specific potential risks to patient and surrogate participants and have developed plans for mitigation.

1. *Concern that access to PD staff and urgent services will change because of research.* We will assure all participants that patients in both groups will have the same access to PD clinic staff for questions or concerns, same as in current practice.
2. *CKD-PD app may not identify overhydration as anticipated.* We will advise patients that they still need to keep all the usual scheduled PD clinic appointments, so participants receive the current standard of care.
3. *We anticipate that CKD-PD app users will receive increased number of clinical interventions as a result of increased monitoring.* We believe this result will improve effectiveness and quality of care, however there is always inherent risk in any clinical intervention even if the benefits are determined to outweigh them. All clinical decisions will be made by the same providers already caring for the patients, according to the usual standard of care. Study clinicians will receive training for interpreting CKD-PD app data

which includes a summary of the local standard of practice, assessing the whole clinical picture, and looking at data trends rather than single isolated readings.

4. *CKD-PD app users may introduce new source of potential error by incorrect data entry.* Patient or surrogate will be given training in proper data entry techniques and observed in their homes to make sure they can use app correctly.
5. *Failure of technology (loss of network connection, malfunction of smart phone) could result in unanticipated delay or loss of data for CKD-PD app users.* We will provide participants in the CKD-PD app group with directions on how to respond to failure of technology. This includes resuming use of the PD logbook and how to notify study staff in the event of technology failure or question on correct use of CKD-PD. This inadvertent data loss is similar to a lost log book in the control group.
6. *CKD-PD app users are at risk for potential unexpected or unintended consequences of introducing a new process or technology.* Study staff will be monitoring the use of CKD-PD, looking for potential issues or problems that were unexpected or unanticipated throughout the study including mismatched expectations among MDs, RNs, and patients.
7. *Loss of confidentiality and or privacy due to loss of data or hardware.* Privacy and confidentiality loss may occur due to data breaches, physical loss or theft of computers, or carelessness of study personnel. We will minimize these threats by using password enabled and encrypted computers, de-identified data where possible, and research ethics training for study participants. The CKDNET and Thai Care Cloud has data safety features built in to its foundational structure including firewalls, encryption, and access restrictions.
8. *Failure to react to life threatening data elements in a timely fashion.* Patients will be informed that the PD clinic will only check PD metrics once a day and be available for calls from patients according the usual practice. We will advise patients that if they detect PD metrics in the action required range or have any concerning symptoms, and are unable to contact the PD clinic, they should proceed as standard practice for PD patients or go to the emergency department.

Plan for medical intervention

In the event of unexpected need for medical intervention, patients will be instructed to contact the PD clinic or emergency room depending on the circumstances. Since all of the participants are currently patients managed in this clinic and in this tertiary care hospital, they will be able to provide any necessary medical intervention. Patients and family members will receive information on how to obtain emergency care during off hours for clinical concerns and critical values of hydration metrics e.g. BP >200/120, BP< 80/40 during the enrollment, in accordance to the usual practice at the PD clinic.

Vulnerable Subjects

Our study does not involve special vulnerable populations such as fetuses, neonates, pregnant women, children, prisoners, institutionalized individuals.

Potential Benefits of the Proposed Research to Research Participants and Others

The objective of this research is to improve early treatment of OH thereby decreasing complications and hospitalizations. If our hypothesis is true, this is a potential benefit to CKD-PD app users. It will also support further efforts to develop and scale up use of CKD-PD app thereby benefiting many more individuals. Patients benefit from accurate and timely monitoring of hydration status as it increases opportunity for meaningful and early intervention. The CKD-PD app also aims to improve patient engagement in self-management of PD by providing a graphical display of PD monitoring metrics similar to a dashboard with trends and current status displays. Patients and their surrogates can gain insight about their own health status and learn how they can work more efficiently with the PD care team to manage their PD and hydration status. Given the minimal risk involved in this study, the anticipated benefits presented are reasonable.

Importance of the Knowledge to be Gained

The knowledge gained from this research is important for several reasons. First, determining whether or not using the CKD-PD app can result in earlier treatment for OH is important before scaling up the intervention to a larger population. Second, the information gained from this research is important preliminary information in order to conduct the research of greatest interest – whether or not use of the CKD-PD app can reduce complications and hospitalizations and decrease mortality for PD patients. If proven successful, this can meaningfully impact the lives of thousands of PD patients and potentially reduce costs. Third, this research will also provide information about whether or not PD patients can successfully self-monitor their hydration status, which is valuable knowledge affecting further implementation of the CKD-PD app to a larger population. Fourth, it will also provide the opportunity to link patient collected mobile health data with hospital and clinic records to provide a rich multi-modal database for predictive analytics. Considering these benefits to individual participants and other PD patients, the risks are reasonable

Monitoring and Quality Assurance

Our project measures the impact of the CKD-app on managing OH. Our intervention is the use of the app, not a specific medication or treatment and all participants will receive the same clinical interventions based on the same usual standard of practice. Therefore, we feel there is low risk to patients as the care and treatment of patients is

standardized- the difference is the timeliness of the interventions. Because our research will introduce a technology that can impact the frequency of clinical interventions and the quality of data used to manage patients, we have outlined several ways to reduce or manage the potential risks. In addition, we will take the following steps to ensure safety.

1. Develop guidelines for PD clinic staff regarding the process of monitoring and response to the daily outlier alerts generated by the CKD-PD web application, and communications from patients or surrogates. These guidelines will provide details on the daily review of hydration metric alerts for “action required”, action steps to be taken (e.g. contact patient, review with nephrologist), recording in study log.
2. Provide a summary of guidelines for managing OH in the study site nephrology clinics based on Thai standards of care to serve as a reference and promote consistency of clinical interventions nephrologists and PD nurses.
3. Develop a process for case review by study investigators (nephrologists) for unexpected complications or hospitalizations, and unexpected increase /decrease in clinical interventions for OH.
4. [name] and [name] will be primarily responsible for oversight of the research activities and data collected at Srinagarind Hospital, Khon Kaen Hospital and Chaiyaphum Hospital. The consortium steering committee comprised of Drs. [name], [name], [name], and [name] will also serve as a data safety monitoring committee and will monitor data during collection for safety signals such as increased complications or mortality in either study groups or other indications of potential concerns. They will be in frequent contact throughout the study via email, video calls, in addition to scheduled site visits. All serious adverse events will be reported to the Srinagarind Hospital/Khon Kaen University Ethics Review Committee and Partners/MGH IRB according to their requirements. Data collection and study activities will be suspended until appropriate precautions have been taken to address or avoid repeat safety concerns
5. We will register with clinicaltrials.gov.

Bibliography and References

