The objective of our proposed study is to determine if use of the CKD-PD app can improve early treatment of overhydration in PD patients. Aim 1 of our research proposal is to optimize the usability of the CKD-PD app. We will employ user surveys based on the Unified Theory of the Acceptance and Use of Technology model, observations using the “Think Aloud” methodology and % completion of hydration metrics. Using these results, we will conduct a process improvement project with 3 rapid cycles to iteratively improve the CKD-PD app usability. In Aim 2, we will conduct a randomized clinical trial comparing the incidence of clinical interventions for treatment of overhydration. PD patients from Srinagarind Hospital, Khon Kaen Hospital, and Chaiyaphum Hospital nephrology clinics in Northeastern Thailand (N=200) will be randomized into two groups – one using the CKD-PD app, and one receiving usual management. Our primary outcome will be the incidence of clinical intervention to treat overhydration as an intermediate outcome related to our secondary outcomes: complications, hospitalizations, and mortality related to fluid overload. We will measure the effect size of the app usage on these secondary outcomes.

Design

Process improvement (Aim 1)

Interventional randomized control trial (Aim 2)

Populations

Study site

Srinagarind Hospital, Khon Kaen University, Khon Kaen Thailand (Aim 1)

Srinagarind Hospital, Khon Kaen Hospital, and Chaiyaphum Hospital (Aim 2)

Aims

Our proposed study objective is to answer the question:

Does the use of the CKD-PD app improve early treatment of overhydration in PD patients compared with those receiving usual care?

Aim 1: Optimize the usability of the CKD-PD app and validate hydration metrics collection with NFC

Aim 2: Conduct a randomized controlled trial to determine if using the CKD-PD app improves early treatment of overhydration by comparing the incidence of clinical interventions to treat overhydration in CKD-PD app users and non-users.

Hypothesis: Use of the CKD-PD app will allow for earlier treatment of OH compared to patients not using the app, thereby potentially reducing complications, hospitalizations, and mortality from congestive heart failure, infections, hypertensive emergencies, and major cardiovascular events.

Background and significance

Chronic kidney disease in Thailand

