
hydration metrics in the CKD-PD app, so patients can monitor their own hydration status 3) access to near real time data and alerts to PD clinic staff about critical abnormalities in patients' hydration metrics, 4) enhanced communication between PD patients and clinic staff, 5) integration of patient collected data from the CKD-PD app with electronic longitudinal health data in the CKDNET database on the Thai Care Cloud. Combining these data types has potential to predict which patients are most likely to need early treatment intervention and serve as a platform for data analytics to improve outcomes.

Aim 1: Optimize the usability of the CKD-PD app and validate hydration metric collection with NFC

Overall study design: This project will involve human subjects research at Srinagarind Hospital for participation in the optimization of the usability of the CKD-PD app, using process improvement methodology. It will involve collecting qualitative data from participant questionnaires and observation, and quantitative data from the CKDNET (Chronic Kidney Disease in NorthEast Thailand) database regarding their use of the CKD-PD app. A multidisciplinary team will review results and make iterative improvements to the CKD-PD based on whether or not the modification is expected to fulfill one or more of the following improvement criteria: 1) ease of use, 2) improved hydration metric monitoring, 3) increased user engagement and benefit, 4) facilitation of patient/provider communication. We have set thresholds after each improvement cycle to define successful optimization (Table 2). We will also compare hydration metrics collected using the CKD-PD app with hydration metrics collected directly by PD staff using usual methods. After completion of the 3 improvement cycles, we will conduct an implementation pilot of the CKD-PD app with a different group of 5 users. They will use the CKD-PD app for 1 week, collecting the same metrics as during the improvement cycles. The goal is to identify training and implementation issues, and assess usability with a different group of users. During the second week, research assistants will visit each participant at home collect hydration metrics, using PD clinic equipment (scales and BP cuffs) and compare with patient collected hydration metrics using CKD-PD app to assess validity of home collected hydration metrics with CKD-PD app.

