6. *Validation of hydration metrics:* During the second week of the implementation pilot, PD clinic staff will conduct a home visit for the 5 participants (Group 2). They will collect hydration metrics directly and compare with the results collected by the participant using CKD-PD. If there is a discrepancy, PD staff will review the hydration metric collection with the participant and check the equipment. After correcting any issues, they will conduct a repeat visit and repeat the process.

Table 2: Summary of Process Improvement Project to Optimize Usability of the CKD-PD app

	Improvement Cycle #1 1 month (N=10)	Improvement Cycle #2 1 month (N=5, Group 1)	Improvement Cycle #3 1 month (N=5, Group 1)
Step 1: Collect data			
Objective	- Introduce CKD-PD app	- Test revised app for 1 week	- Test revised app again 1 week
Method	- Structured interviews - In-clinic observation	- “Think Aloud” in home testing	- “Think Aloud” in home testing
Metrics	- Score on UTAUT structured interview - Observation summary	- Average feature rating - % completion of data entry - # & type of clinic contacts	- Average feature rating - % completion of data entry - # & type of clinic contacts

Step 2: Identify improvement opportunities, determine app modifications, and training needs with team

Step 3: Revise CKD-PD app and re-test

Optimization goal	Collect baseline rating of features	- Average feature rating <2.5 ->70% data fields complete	-Average feature rating <1.5 ->90% data fields complete
Deliverable	- Revised app - User training needs	- Revised app - Draft user training materials	- Final app revision - Final training guide & video

Potential risks to participants All results will contain patient identifiable data. We believe this study will have low risk to participants with regard to physical, psychological, social, cultural or legal aspects. Potential risks exist due to loss of privacy and concern about change or access to PD care have been specifically identified. Technological problems may expose users to risk through failures of notification of the PD care team or patient of outlier results, misunderstood expectations, or unintended consequences. Strategies to mitigate these risks are discussed below. Alternative strategies available to participants are the option to decline or withdraw from the project at any time.

Protection Against Risks

Informed Consent and Assent

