Trained research staff will obtain informed consent from all participants. [name] and [name] will oversee this process, including training of research staff and answering any questions from staff or participants as needed. The informed consent form and process will be approved by the Khon Kaen University Ethics Committee and the Partners Health Care/Massachusetts General Hospital Institutional Review Board. All participants will be informed that their participation is voluntary and does not in any way impact access to treatment or other resources for care, and they can drop out of the study at any time for any reason. Signed copies of the informed consent will be kept with study records, and given to the participant.

Planned strategies to minimize potential risks:

We will include the following general protections:

1. De-identify and summarize results from questionnaires, observations, interviews, and the CKD-PD database when possible prior to sharing this information with the CKD-PD app process improvement team.
2. Confirm all study staff successfully completed CITI ethics training
3. Provide all written materials and descriptions of study activities in local language (Thai) at an appropriate literacy level.
4. The CKD-PD app and validation of application from phase I study will be reported to the Khon Kaen University Ethics Committee before apply to participants in phase II study.

We will obtain IRB approval for this proposed research through the Khon Kaen University Ethics Committee and the Partners Health Care/Massachusetts General Hospital Institutional Review Board. We will not begin enrollment until this has been secured.

We have identified these potential risks and have developed plans for mitigation.

1. *Loss of confidentiality and or privacy due to loss of data or hardware:* Privacy and confidentiality loss may occur due to data breaches, physical loss or theft of computers, or carelessness of study personnel. We will minimize these threats by using password enabled and encrypted computers, de-identified data where possible, and research ethics training for study participants. The CKDNET and Thai Care Cloud has data safety features built in to its foundational structure including firewalls, encryption, and robust access restrictions.

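### The Aim 1 home-visit check cannot isolate NFC transfer, and the plan does not say whether its result is taken before or after correction

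*Combined protocol and SAP*

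**What the plan says.** The heading of the Aim 1 section states the goal: "Optimize the usability of the CKD-PD app and validate hydration metric collection with NFC". The list of aims near the start of the protocol says nearly the same.

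The accuracy work sits in the implementation pilot with the 5 participants of Group 2. The Aim 1 overall study design says of them: "They will use the CKD-PD app for 1 week, collecting the same metrics as during the improvement cycles". In the second week they are visited at home, where their metrics are taken "using PD clinic equipment (scales and BP cuffs) and compare with patient collected hydration metrics using CKD-PD app". That paragraph gives the purpose as "to assess validity of home collected hydration metrics with CKD-PD app".

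Item 6 of the planned research procedures adds what happens after a discrepancy. Staff go over the collection with the participant and check the equipment. Then: "After correcting any issues, they will conduct a repeat visit and repeat the process".

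The plan does not define a discrepancy, name an agreement statistic or acceptance limit, say whether the two readings are paired in time, cap the number of repeats, or say which visit is reported. The goals in Table 2 concern feature ratings and completeness of data fields. NFC entry otherwise appears in Aim 1 only as a task to be observed for usability (item 2).

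The result has a use. Under the Aim 1 risk-mitigation strategies (item 4), the "validation of application from phase I study will be reported to the Khon Kaen University Ethics Committee" before the app is applied in the second phase.

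**The concern.** NFC carries a value from the home device to the phone. To validate that step, one has to compare what the device showed with what was stored, for the same reading. The plan instead compares two readings that differ in device, operator and possibly time. A difference may come from any of these, so neither agreement nor disagreement says much about the transfer.

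A separate weakness is that correction and revisiting apply only to discrepant cases, with no rule on which visit counts. If the final visits were reported, the result would describe home readings after staff had dealt with the disagreements.

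At stake is what the ethics committee can conclude before Aim 2. There, app readings outside the action-required limits open a route to primary-outcome interventions that only the app group has (Aim 2, Clinical interventions). The Aim 2 risk section itself lists incorrect data entry as a possible new source of error for app users.

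**Working it through.** The plan gives no figure for the validation, so there is nothing to reproduce. The inputs from the documents are the 5 participants, clinic versus home equipment, and the repeat rule. Every SD, cut-off and discrepancy probability below is an assumption for illustration.

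**1. What each comparison contains**

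| Source of a difference | Staff reading vs patient's app reading | Home-device display vs stored value, same reading |
|---|---|---|
| Variation between separate readings | yes | no |
| Clinic device vs home device | yes | no |
| Staff vs patient technique | yes | no |
| Transfer of the value | yes | yes |

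Only the second comparison leaves the transfer by itself, and no step in the plan makes it.

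**2. How often a flawless transfer would look discrepant**

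Take systolic BP with a within-person SD s between separate readings and a cut-off of 10 mmHg. The SD of a difference is s√2, and P(|d| > 10) = 2[1 − Φ(10/(s√2))].

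| s (mmHg) | s√2 | P(\|d\| > 10) |
|---|---|---|
| 5 | 7.07 | 0.157 |
| 8 | 11.3 | 0.377 |
| 12 | 16.97 | 0.556 |

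**3. How often a real transfer error in weight would be flagged**

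Let the difference between the two weighings have SD σ, and flag it beyond 1.96σ (a 5% false-flag rate). For a transfer error e, P(flag) = 1 − [Φ(1.96 − e/σ) − Φ(−1.96 − e/σ)].

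| e (kg) | σ = 0.3 kg | σ = 0.5 kg | σ = 1.0 kg |
|---|---|---|---|
| 0.5 | 0.385 | 0.170 | 0.079 |
| 1.0 | 0.915 | 0.516 | 0.170 |
| 5.0 | 1.000 | 1.000 | 0.999 |

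Gross errors are seen. A 0.5 kg error is missed more often than not at every σ shown.

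**4. What the repeat rule does if the last visit is reported**

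Let each visit show a discrepancy with probability p by chance alone, with nothing truly repaired. Agreement per participant is 1 − p at the first visit and 1 − p² after one repeat of discrepant cases. For all 5 to agree, raise each to the fifth power.

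| p | Per participant, first visit → after one repeat | All 5, first visit → after one repeat |
|---|---|---|
| 0.1 | 0.90 → 0.99 | 0.590 → 0.951 |
| 0.2 | 0.80 → 0.96 | 0.328 → 0.815 |
| 0.3 | 0.70 → 0.91 | 0.168 → 0.624 |
| 0.5 | 0.50 → 0.75 | 0.031 → 0.237 |

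If first-visit results are reported, the left-hand values apply and there is no inflation.

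**5. What 5 participants can show at best**

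With 0 discrepancies in 5, the exact upper 95% limit for the per-participant discrepancy rate is 1 − 0.05^(1/5) = 0.451 one-sided, or 1 − 0.025^(1/5) = 0.522 two-sided. A fault present in 10% of participants appears in at least one of 5 with probability 1 − 0.9⁵ = 0.41; one present in 20%, with probability 1 − 0.8⁵ = 0.67.

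**The case against.** The best defence is that this is a five-person pilot inside a process-improvement project, not a formal agreement study. Its stated goal is to bring out training and implementation problems, and finding, fixing and retesting is how such a project works. The purpose given for the visit is the validity of home-collected metrics as a whole. For that, clinic equipment against home readings is a reasonable comparison, and device and technique error belong in it. This stands for the end-to-end purpose. It does not answer the NFC aim, which the section heading states expressly.

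Three stronger readings are tempting, and the documents do not support them.

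- A reader might infer that the procedure produces agreement by construction. Item 6 does not say that post-correction visits are the reported result or that first-visit data are discarded. A persistent fault would not become agreement on repetition, and agreement after a genuine repair is real for the repaired set-up. Different devices and separate readings also push towards disagreement, the opposite direction.
- A reader might infer that NFC is not tested at all. The transfer is part of the chain compared, and step 3 shows that a gross error would appear.
- A reader might infer that faulty readings pass straight into the primary outcome. In Aim 2 a nurse reviews metrics and symptoms, a nephrologist decides, and a contact without a change in management does not count. App-group homes are also visited to confirm set-up and use, so post-correction agreement has some bearing on Aim 2 conditions. However, no reference measurement is described for that visit.

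The illustrative SDs and the 10 mmHg cut-off come from outside the plan, and the size of the problem depends on them.

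**Conclusion.** The point holds as a limitation of what Aim 1 can claim. The check is end to end. It would reveal gross transfer errors, but it cannot attribute a discrepancy to NFC and would usually miss a small transfer error (a 0.5 kg error flagged with probability 0.08 to 0.38, for an assumed SD of 1.0 to 0.3 kg).

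The repeat rule is a conditional risk. Agreement is overstated only if post-correction results are what is reported, and the plan leaves that open. Under the chance-only assumption with p = 0.1 to 0.3, the probability of full agreement would then rise from 59% to 95% or from 17% to 62%.

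The Aim 2 sample size and primary analysis do not change. The matter deserves action because a direct test of the stated NFC aim fits into a visit already planned.

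**What to change.** Amend item 6 of the Aim 1 research procedures as follows.

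1. At the home visit, write down the value shown on the patient's home device for each reading: weight, systolic and diastolic BP, and the raw inflow and outflow readings. The raw readings are needed because ultrafiltration volume is a calculated difference. Compare each with the value stored for that same reading and report this as the NFC transfer result. The value in the app isolates NFC; the value in CKDNET adds the internet upload. Apart from any rounding, they should be identical.
2. Keep the clinic-versus-home comparison as the end-to-end result. State beforehand what counts as a discrepancy, report first-visit paired differences before any correction, and report post-correction results separately as a training or equipment outcome.
3. State the result as coming from 5 participants, with the exact limit in step 5 of the working.

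While editing, reconcile who makes the visit: the overall study design says research assistants, item 6 says PD clinic staff.

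The cost is a few sentences and an extra column on the visit form, with the stored values looked up. No visits are added. The drawback is that the reported agreement may look less favourable.
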